10.6. Microbiological testing

Results from standard of care testing. Microbiological tests according to standard of care from site.

Known previous colonization with multidrug resistant microorganism.

Known previous SARS-CoV-2 infection if required hospitalisation and data is available

- Type of samples collected: blood, ETA, BAL, pleural fluid, urine
- Type of tests: cultures, recording quality sputum (<10 epithelial cells and >25 leukocytes per field magnification x 100), antigen detection, antibody detection, molecular testing
- Test results: list of microorganisms. Selected susceptibility patterns

Susceptibility testing will be grouped based on antimicrobial resistant phenotypes definitions: methicillin resistant *Staphylococcus aureus* –MRSA-, carbapenem resistant Enterobacteriaceae, Extended Spectrum Beta Lactamases Enterobacteriaceae –ESBL-, carbapenem non susceptible *Pseudomonas aeruginosa*, multidrug resistant *P.aeruginosa*. (Based on <https://www.cdc.gov/nhsn/PDFs/pscManual/11pscAURcurrent.pdf>)

The data collected will allow also reporting pathogens of public health interest.

Within VALUE-Dx WP3 there is current work on inter-operability with lab devices, with the objective to achieve direct connectivity with these systems to have antimicrobial resistance information from lab results easily available.

Study samples. For diagnostic intervention: nasopharyngeal swab; endotracheal aspirate, spontaneously produced sputum collected as standard of care. Specific procedures for collection and processing will be provided. Data to be recorded:

- Test result (including data on genomic copies provided by the test)
- Time at which Test Result was Generated
- Time at which Test Result was received by care team and how it is communicated
- Time at which antibiotics were prescribed
- Results from standard of care diagnostic tests (e.g. cultures) with comparable targets and assessment of discrepant results

10.7. Qualitative evaluation

A qualitative process evaluation will be nested within the trial. The process evaluation will capture data to understand how clinicians adopt and experience RSDTs when delivering care in ERs. Related documents will be also be sent for ethical approval.

Recruitment: We will select 3-6 trial sites, sampling where possible to get sites from a range of countries. Once a site has completed recruitment for the trial, or once a site has had the RSDTs for at least 2 months, we will ask the PI at each site to identify 2-8 healthcare professionals who would be willing to share their experiences of taking part in the trial. Healthcare professionals will include clinicians working in the emergency department with the main criteria for inclusion in interviews being that clinicians should have used the RSDTs at their site. Potential clinician participants will be contacted in person or by email by the PI or another member of the research team. Emails will include further study information.

Sampling for clinician interviews will likely be by convenience and snowball sampling, through the site PIs, with colleagues recommending others who may be interested in participating in an interview. If there is a good response rate the research team will purposively select participants

based on site, site patient recruitment and use of RSDTs and job role. We will aim to complete 20-25 interviews with clinicians. All participants will only be required to take part in a single interview and a 15 euro voucher will be provided for each participant as reimbursement for their time.

Interviews: Interviews will be conducted by telephone (or alternative means such as Skype teleconferencing) and all participants will be asked to provide verbal consent prior to the interview starting. Interviews may be carried out in person if suitable and, if so, written informed consent will be sought. The researcher will make a written record of this consent. Interviews will be audio-recorded with participants permission. All interviews will be expected to last approximately 30-45 minutes. Clinician interviews will follow a clinician topic guide and will ask about experiences of using RSDTs in usual practice, interpreting results and the impact of results on patient management and clinical decision making.

11. TRAINING

11.1. Good Clinical practice training

The Principal Investigator of a study site needs to provide a valid ICH-GCP certificate to timely identify and enrol eligible patients, collect informed consent forms, collect source data, enter data into clinical database. See the ADEQUATE monitoring plan for more details. Guidelines will preferably follow ISO20916:2019 because of the specific differences in device related events and deficiencies reporting.

11.2. Medical Device training, being part of the Site Initiation Visit.

Training of the hospital staff involved in the study will be implemented, with an emphasis on sample collection, sample processing, correctly identifying causative organisms and performance of susceptibility testing in coordination with bioMérieux. Where required, guidance will be provided to improve procedures and align them with standardized uniform manners following the principles of Good Clinical Laboratory Practice (GCLP). Quality Control of the device will be performed as described in the ADEQUATE monitoring plan.

11.3. Data management training

All sites will be trained to use the data management system (Research Online) as part of the site initiation visit. To assure high quality, the Data Management Department of the Julius Centre (JC) of UMCU works according to a Quality Management System. All work is carried out in accordance with UMCU written Standard Operating Procedures (SOP) and Work instructions.

12. SAFETY REPORTING

12.1. Adverse events

Definitions

Adverse Event (AE)

For this study, an adverse event is defined as any untoward medical occurrence, inappropriate patient management decision, unintended disease or injury, or untoward clinical signs in patients, users, or other persons, with any connection to study related activities, whether or not related to the IVD medical device.

Adverse device effect (ADE)

An adverse event related to the use of the BioFire®.

Serious Adverse Event (SAE)

All SAEs, regardless of relationship to the study device or procedure will be documented in the source. It is the Investigator's responsibility to determine the "seriousness" of an AE using the protocol defined terms, listed below. A SAE is an AE that results in one or more of the following for this study:

- Resulted in death: An AE that resulted in the patient's death.
- Life-threatening illness or injury: The patient was at imminent risk of dying at the time of the adverse event.
- Permanent impairment: An AE that resulted in permanent impairment of a body function, including chronic diseases or permanent damage to a body structure.
- Required in-patient or prolonged hospitalisation.
- Resulted in medical or surgical intervention to prevent life threatening illness or injury or permanent impairment to a body structure or body function.
- Led to fetal distress, fetal death or congenital abnormality or birth defects, including physical or mental impairment.

Notes:

1. Hospitalisation on Day-1 should not be reported as an AE or SAE if this is a direct consequence of the initial referral to the hospital.
2. SAEs resulting in death should be reported using the primary cause of death as the event term. The only exception is "Sudden Death" when the cause is unknown.
3. Planned hospitalisation for a pre-existing condition is not considered a SAE.

Serious adverse device effect (SADE)

Adverse device effect that has resulted in any of the consequences characteristic of a serious adverse event.

Categories of adverse events

ADVERSE EVENTS	Non-device-related	Device-related
		Applies to: - Inaccurate test result leads to indirect harm to the patient - Device causes direct harm to user or another person
Non-serious	Adverse event	Adverse device effect
Serious	Serious adverse event	Serious adverse device effect

SEVERITY OF ADVERSE EVENTS

It is the Investigator's responsibility to assess the severity of an AE. A change in severity may constitute a new reportable AE.

Also, the following guideline should be used to determine the severity of each adverse event:

- **MILD:** Awareness of signs or symptoms, but does not interfere with the patient's usual activity, or is a transient event that resolves without treatment and with no sequelae.
- **MODERATE:** A sign or symptom, which interferes with the patient's usual activity.
- **SEVERE:** Incapacity with inability to do work or usual activities.

RELATIONSHIP OF ADVERSE EVENTS

It is the Investigator's responsibility to assess the relationship between all AEs to the study device and procedure. The following guidelines should be used in determining the relationship of an AE to a device, procedure, or other causality

Not related	
Relationship to the procedures or device can be excluded when:
 
• The event is not a known side effect of the product category the device belongs to or of similar device and procedures;• The event has no temporal relationship with the use of the device or the procedures;• The event involves a body-site or an organ not expected to be affected by the device or the procedure or the disease under investigation;• The event can be attributed to another cause (e.g. an underlying or concurrent illness/clinical condition, an effect of another device, drug, treatment, or other risk factors);• Harms to the patient are not clearly due to use error; or• To establish the non-relatedness, not all the criteria listed above might be met at the same time, depending on the type of device/procedure and the event.
Unlikely	The relationship with the use of the device seems not relevant and/or the event can be reasonably explained by another cause, but additional information may be obtained.
Possible*	The relationship with the use of the device is weak but cannot be ruled out completely. Alternative causes are also possible (e.g. an underlying or concurrent illness/condition and/or an effect of another device, drug, or treatment). Cases where relatedness cannot be assessed, or no information has been obtained should also be classified as possible.

Probable*	The relationship with the use of the device seems relevant and/or the event cannot reasonably be explained by another cause, but additional information may be obtained.
Causal Relationship*	
The event is associated with the device or with procedures beyond reasonable doubt when:
 
 • The event is a known side effect of the product category the device belongs to or of similar device and procedure • The event has a temporal relationship with the device uses/application or procedures • The event involves a body-site or organ that 
 ◦ The device or procedures are applied to ◦ The device or procedures have an effect on • The event follows a known response pattern to the medical device (if the response pattern is previously known) • Other possible causes (e.g. an underlying or concurrent illness/clinical condition and/or an effect of another device, drug, or treatment) have been adequately ruled out • Harm to the patient is due to error in use • To establish the relatedness, not all the criteria listed above might be met at the same time, depending on the type of device/procedure and the event.

*Denotes “related” to the study procedure or device and should be reported (AE) as part of the study.

12.2. Reporting Adverse Events

The principal investigator shall:

- record all AEs and device deficiencies, regardless of relationship to the study device or study procedure in the source, together with an assessment as to whether the device or study procedure were a cause of the event,
- report to the Sponsor, without unjustified delay (max. 48 hours after becoming aware of the event), all SAEs, that deemed to have a possible, probable, or causal relationship to the study procedure, disease under investigation or device, from the time of signing the informed consent through study completion (day-30 for the main study or 6 months for the extension study) and device deficiencies that could have led to a SADE; this information shall be promptly followed by detailed written reports, as specified in the Safety Management Plan,
- report to the Sponsor, without unjustified delay (max. 7 calendar days after becoming aware of the event), all AEs, that deemed to have a possible, probable, or causal relationship to the study procedure or device from the time of signing the informed consent through study completion (day-30 for the main study or 6 months for the extension study); this information shall be promptly followed by detailed written reports, as specified in the Safety Management Plan,
- ensure expedited reporting to the ethics committee, or per the timelines of the national regulations, SAEs that deemed to have a possible, probable, or causal relationship to the study

procedure, disease under investigation or device, from the time of signing the informed consent through study completion (day-30 for the main study or 6 months for the extension study) and device deficiencies that could have led to a SADE, when required by the national regulations or Safety Management Plan or by the ethics committee,

e) ensure annually reporting to the ethics committee, or per the timelines of the national regulations, AEs that deemed to have a possible, probable, or causal relationship to the study procedure or device, from the time of signing the informed consent through study completion (day-30 for the main study or 6 months for the extension study), when required by the national regulations or Safety Management Plan and

f) ensure to report to regulatory authorities, SADEs and device deficiencies that could have led to serious adverse device effect, as required by national regulations, and supply the Sponsor, upon Sponsor's request, with any additional information related to the safety reporting of a particular event. Sponsor remains responsible for adequate reporting to regulatory authorities.

The study site will report applicable safety events to the Sponsor by entering the event into the AE form in the eCRF, which will trigger an automated email to the Sponsor and manufacturer. Refer to the ADEQUATE Safety Management Plan for more extensive guidance on reporting.

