 - For initially non-admitted patients: any admission or death within 30 days
 - For initially hospitalised patients: i) any readmission, ii) ICU admission ≥ 24 hours after hospitalisation, or iii) death within 30 days

Nature and extent of the burden and risks associated with participation, benefit and group relatedness: Participation in the study involves collection of data that can be obtained from medical charts and follow up questionnaires and interviews. Respiratory samples (e.g. nasopharyngeal swab, sputum) will be obtained as standard of care and diagnostic intervention (Biofire FilmArray) will be used only for participants randomised to the intervention. Based on the results of diagnostic testing (BioFire FilmArray) antibiotics may be withheld when deemed unnecessary, or a different antibiotic class may be selected when certain bacterial pathogens are detected. The risks and benefits of management decisions, complemented with adequate training, are subject to the current investigation.

3. GENERAL CONSIDERATIONS WORK PACKAGE 4 AND VALUE-Dx OVERVIEW

The purpose of VALUE-Dx consortium (www.value-dx.eu) is to facilitate and accelerate the rigorous assessment and implementation of (new) diagnostic technologies into healthcare settings, by establishing the infrastructure, methods, processes and approaches needed to understand, evaluate, assess, and demonstrate the multi-faceted value of diagnostics and overcome the associated barriers to their widespread adoption and use. VALUE-Dx focuses its research on **community acquired acute respiratory tract infections (CA-ARTI)**.

The objectives of VALUE-Dx are:

- To design a health-economic framework to assess and demonstrate the value of diagnostics both for individual patients and for public health impact by reducing antibiotic use and subsequent antibiotic resistance among patients;
- To establish a sustainable European Standardised Care Network adequately trained and resourced to conduct clinical trials evaluating the value of diagnostics;
- To design and implement clinical studies to demonstrate the value of diagnostics in the optimal management of CA-ARTIs;
- To explore, define and attempt to resolve the psychological, ethical and social barriers which prevent the more widespread adoption of diagnostics delivering healthcare to the population.

The clinical studies, to be implemented in WP4, aim to gather evidence on:

- i) doses or days of antibiotics prescribed,

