10.2. Randomisation and blinding

Due to the nature of the intervention, blinding is not possible. After all eligibility criteria have been verified and informed consent has been obtained, randomisation will be performed using the built-in randomisation module of the eCRF system. Allocation will be concealed until the moment of randomisation. To this end, block randomisation will be used with variable blocks of size 2, 4 and 6. Randomisation will be stratified by centre. After the decision to randomise the patient is made, patients will not be excluded from the trial. If the allocated intervention is not applied for any reason, this will be recorded and follow-up for the participant will be completed.

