12.5. Data Safety monitoring board (DSMB)

A Data Safety Monitoring Board has been established with the aim to safeguard the interests of trial participants, assess the safety of the interventions during the trial, and monitor the overall conduct of the trial. A specific charter document describes the roles and responsibilities of the independent DSMB for the ADEQUATE trial, including the timing of meetings, methods of providing information to and from the DSMB, frequency and format of meetings, statistical issues and relationships with other committees.

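### Adverse-event form counts pass through an unblinded relatedness filter tied largely to a device used in one arm, so they are not a valid between-arm comparison (minor)

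*Combined protocol and SAP*

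**What the plan says.** Section 12.1 defines an adverse event as one "with any connection to study related activities, whether or not related to the IVD medical device". For serious events it adds: "All SAEs, regardless of relationship to the study device or procedure will be documented in the source". Section 12.2 likewise has all adverse events recorded in the source regardless of relationship.

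Reporting is narrower. Under 12.2, what goes to the sponsor within 7 days is "all AEs, that deemed to have a possible, probable, or causal relationship to the study procedure or device". Serious events go within 48 hours if related to the study procedure, the device or the disease under investigation. Sites report applicable events by entering them on the eCRF adverse-event form, and each entry triggers an automatic email to the sponsor and the manufacturer.

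On who judges, 12.1 states: "It is the Investigator's responsibility to assess the relationship between all AEs to the study device and procedure". Section 10.2 states: "Due to the nature of the intervention, blinding is not possible". The Summary says the "diagnostic intervention (Biofire FilmArray) will be used only for participants randomised to the intervention". For unclear cases 12.1 directs: "Cases where relatedness cannot be assessed, or no information has been obtained should also be classified as possible". Section 12.5 gives the DSMB the task to "assess the safety of the interventions during the trial".

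**The concern.** A relatedness filter is neutral between arms only if both arms have the same things to be related to, or if the person assessing relatedness does not know the allocation. Neither holds here. A control patient has no device, and respiratory samples are standard of care (Summary; 10.3), so little remains under the study-procedure limb beyond consent, data collection and follow-up contacts. In the intervention arm the device is always a candidate cause, and doubtful cases default to reportable.

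The protocol sees this hazard elsewhere. Section 7.1 rejects cause-specific readmission and cause-specific death as outcomes because the trial is not blinded. Section 12.2 then makes entry on the adverse-event form depend on cause.

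At stake are the harms that the co-primary composite does not count: non-serious events, including drug reactions (section 4.1 gives avoiding drug-related adverse events as a reason for more judicious prescribing); serious events in initially hospitalised patients that lead to no readmission, no ICU admission at 24 hours or later and no death; and events after day 30 in the extension study.

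**Working it through.** **1. The main safety comparison, as planned.** Inputs from 13.1: incidence 10% in both arms, margin 5 points, one-sided alpha 0.05, power 0.95.

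n per arm = (z₀.₉₅ + z₀.₉₅)² × 2p(1−p) / margin² = (1.645 + 1.645)² × 0.18 / 0.0025 = 10.82 × 72 ≈ 779.2, rounded up to **780**, as stated. At 5% incidence: 10.82 × 0.095 / 0.0025 ≈ 411.2, rounded up to **412**, as stated. With 800 per arm at 10%, the standard error is √(0.18/800) = 0.015 and power is Φ(0.05/0.015 − 1.645) = Φ(1.688) ≈ 95.4%.

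This endpoint has no causality condition (6.1) and is compared by allocated arm with a 90% CI (13.2, 13.3). The filter in 12.2 does not touch it.

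**2. Routes onto the adverse-event form, by arm (12.1, 12.2).**

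| Event | Intervention arm | Control arm |
|---|---|---|
| Non-serious, device-related | reportable | route does not exist |
| Non-serious, procedure-related | reportable | reportable, few procedures |
| Serious, disease-related | reportable | reportable |
| Serious, device-related | reportable | route does not exist |
| Neither device, procedure nor (if serious) disease | source only | source only |

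In 12.1 the *Unlikely*, *Possible* and *Probable* grades are worded around use of the device, which sharpens the asymmetry.

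**3. What unequal capture would do (all rates assumed).** With a common true rate t and capture fractions c_I and c_C, the difference seen on the form is t × (c_I − c_C), although the true difference is zero. Take t = 10%, 780 per arm (78 true events in each) and c_I = 50%:

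| c_C | Intervention on form | Control on form | Spurious difference |
|---|---|---|---|
| 50% | 39 (5.0%) | 39 (5.0%) | 0 |
| 25% | 39 (5.0%) | 19.5 (2.5%) | 2.5 points |
| 10% | 39 (5.0%) | 7.8 (1.0%) | 4 points |
| 0% | 39 (5.0%) | 0 (0%) | 5 points |

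For t from 5% to 20% and c_C from 25% to 0%, the range is 0.05 × 0.25 = 1.25 points to 0.20 × 0.50 = 10 points. If both capture fractions are near zero, the difference vanishes and the events are simply not measured. The documents give neither fraction and no event rate.

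**4. Which events are entered digitally.** Section 12.2 sends only applicable events to the form. Section 10.4 lists adverse events in the clinical data set with no causality limit. Section 15.2 says all study information except consent data is entered digitally. These do not agree.

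**The case against.** The strongest reply is that safety in this trial does not rest on the adverse-event form. The co-primary adverse outcome covers every randomised patient, is objective by design and is powered at 95%. That stands. A reader might infer that the trial's safety data as a whole cannot be compared between arms; the documents do not support this. Serious events are not one-sided by construction either, since the disease limb applies equally to controls, although the judgement is still unblinded.

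No section says that the DSMB or the final report will compare adverse events by arm. Section 13 plans no such comparison, and the DSMB charter and Safety Management Plan are cited but not available here, so fuller collection or a different presentation cannot be ruled out. This also stands, and it limits the point to how the form data may be used.

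The filter is partly deliberate: 15.4 describes a risk-adapted approach to safety reporting, and 11.1 and 14.1 refer to ISO 20916. That justifies limiting expedited notices. It does not make the filtered counts comparable.

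A reader might also infer that the filter reverses the sign for antibiotic reactions. Suppose reactions occur in 5% of treated patients, with 70% of controls and 60% of the test arm treated and 800 per arm: 800 × 0.70 × 0.05 = 28 true events against 800 × 0.60 × 0.05 = 24. If 20–50% of the 24 were called device-related, 5 to 12 would be reported, against about none in controls. Nothing in the documents supports 20–50%. Section 12.1 ties device-related patient harm to an inaccurate test result and lists attribution to another drug as a ground for *Not related*, so low capture in both arms is at least as plausible.

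**Conclusion.** The point holds in limited form. Adverse-event form counts, chiefly of non-serious events and of serious events not attributed to the disease, are selected by an unblinded judgement tied largely to a device that one arm never receives. They are not a valid between-arm comparison. The all-cause co-primary endpoint is unaffected, and disease-related serious events are reportable in both arms. The size and direction of any distortion cannot be derived; the 1.25 to 10 points above illustrate assumed rates and are not an estimate.

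The conclusion assumes that 12.2 governs what is entered on the form, which 10.4 and 15.2 leave unclear, and that the unseen Safety Management Plan does not widen collection. Severity is minor, because the main safety inference does not depend on these data.

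**What to change.** - In 12.2, have all serious adverse events entered on the eCRF in both arms whatever their causality, and tabulated by allocated arm for the DSMB and the final report.
- Keep the relatedness filter only for the 48-hour and 7-day sponsor notices and the ethics-committee reports. Restrict the automatic email to events that pass it.
- State that non-serious counts from the form stay filtered by relatedness and are not to be compared between arms.
- Reconcile 10.4, 12.2 and 15.2 on which events are entered digitally.

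The cost is a short amendment to the protocol and the Safety Management Plan, plus some extra eCRF entry for events that sites must already document in the source. No visit or test is added. Collecting every antibiotic-related event, or widening the adverse-event definition, would go further. The former needs a causality judgement of its own and the latter adds events that sites need not now record, so given the risk-adapted approach in 15.4 both are a debatable trade-off and are not part of this recommendation.
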